5.1 Product Features

1. Safe and hygienic: disposable, preventing cross infection.
2. Easy to use: simply take one capsule each time
3. Painless and non-invasive: the use process is painless and non-invasive
4. No side effects: the capsule produces physical stimulation to provoke the intestine's natural peristaltic wave, free of any toxic side effects.

5.2 Product Composition, Working Principle, and Action Mechanism

5.2.1 Structural Characteristics

Main parameters of Vibrabot capsule: nominal diameter: $11.8\pm1\text{mm}$; nominal length: $26.7\pm1\text{mm}$; nominal weight: $4.5\pm1\text{g}$.

5.2.2 Working Principle

After the patient swallows the Vibrabot capsule, the capsule runs through the stomach → duodenum → jejunum and ileum → colon. According to the clinical data and configuration settings, the capsule will reach the colon and vibrate 8 hours after activation for ≥ 180 minutes in a cycle at low, medium, and high frequencies sequentially. The capsule relieves and treats constipation by massaging the colon wall through motor vibration to relieve colon muscle spasms and promote colonic peristalsis.

6. Selection of Subjects

6.1 Inclusion Criteria

1. Patients who can be diagnosed with functional constipation according to the Rome IV criteria.
2. Patients who consent to participate in this trial and voluntarily sign the informed consent form (ICF).

6.2 Exclusion Criteria

1. People who are not eligible for surgery or refuse to undergo any abdominal surgery;
2. People with known or suspected gastrointestinal obstruction, stenosis, diverticulum, bleeding, malformation, and fistula.
3. People allergic to polymeric materials;

4. People implanted with cardiac pacemakers and using gastrointestinal pacemakers;
5. People with abdominal aortic aneurysms, gastrointestinal vascular lesions, ulcers, and lesions with bleeding tendencies.
6. People with dysphagia;
7. Pregnant women;
8. People with severe depression and anxiety and severe acute gastrointestinal lesions.
9. People with other conditions, so the investigator considers them not eligible for this study.

7 . Overall Design

This study is a multi-center, prospective cohort study based on real-world clinical trial design, planning to include 300 patients with chronic functional constipation to treat with Vibrabot capsules, and concurrently include ≥ 300 patients with functional constipation to treat by other methods.

During the study, it is necessary to collect the patient's basic information, baseline constipation status and treatment information, capsule intake during treatment, and concomitant medication. During the treatment phase, patients follow the doctor's advice to receive Vibrabot capsule treatment and maintain stable dietary intake and exercise according to the constipation diagnosis and treatment guidelines.

During the study, the patients need to scan the QR code or search for the electronic questionnaire "Vibrabot Health" Official Account on WeChat, and fill in the relevant information during the treatment in the electronic questionnaire in a timely and truthful manner. The treatment effect of the patients is evaluated by assessing the number of occurrences of spontaneous bowel movements (SBM) and complete spontaneous bowel movements (CSBM).

Note:

[figure not shown]
Spontaneous bowel movement: No medication used within 24 hours before bowel movement.

Spontaneous bowel movement: No medication was used within 24 hours before defecation, and there is a feeling of complete fecal evacuation.

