3.1 Purpose of the Clinical Trial

Through this real-world study, to analyze the response of functional constipation patients with different severity, treatment status, capsule dosage, and combined medication to Vibrabot capsule, as well as the duration of efficacy maintenance during the follow-up period; to compare the efficacy with patients treated with drugs or other therapies during the same period, explore the possibility of curing functional constipation patients, further improve the treatment satisfaction of constipation patients, and promote the establishment and application of consensus or guidelines for the use of Vibrabot capsule in treating functional constipation.

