3.2 Content of the Clinical Trial

This study is a multi-center clinical trial. Patients are considered eligible for this study if they meet the inclusion criteria and do not meet any of the exclusion criteria. This study plans to include 300 patients with chronic functional constipation to treat with Vibrabot capsules for at least 6 weeks, and ≥ 300 patients with constipation receiving

other treatments concurrently. The patients, based on their treatment needs and preferences, and after comprehensive consideration by clinical doctors, will undergo vibrating capsule treatment, other treatments, or combination therapy. After entering the study, patients should maintain stable dietary intake (including high-fiber diet, fiber supplements, probiotics, etc.) and exercise according to the recommendations of the constipation diagnosis and treatment guidelines.

During the entire clinical study period, patient-related information will be collected according to the specified time points in the protocol to evaluate the response of functional constipation patients with different severity levels to Vibrabot capsules.

Patients are considered eligible for this study if they meet the inclusion criteria and do not meet any of the exclusion criteria. This study plans to include 300 patients with chronic functional constipation to treat with Vibrabot capsules for at least 6 weeks or more.

The patients, based on their treatment needs and preferences, and after comprehensive consideration by clinical doctors, will undergo vibrating capsule treatment. After entering the study, patients should maintain stable dietary intake (including high-fiber diet, fiber supplements, probiotics, etc.) and exercise according to the recommendations of the constipation diagnosis and treatment guidelines.

4. Background of the Clinical Trial

Constipation is characterized by a decrease in bowel movements, dry and hard stools, and difficulty in defecation. With changes in diet, faster pace of life, and social psychological factors, the prevalence of chronic constipation is on the rise. The global incidence of chronic constipation is 14%, while the prevalence of chronic constipation in adults in China is 4.0% to 10.0%. The prevalence of functional constipation in China is 6%. The high-risk groups for constipation include the elderly, women,

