diabetics, those taking opiates, antipsychotic drugs, or bedridden patients. Occupation, lifestyle, dietary habits, mental health, family history of constipation, and BMI are factors related to constipation.

Constipation affects patients' quality of life, and some patients abuse laxatives or repeatedly seek medical treatment, increasing medical costs. The main treatments for constipation are adjusting lifestyle, medication, psychotherapy, biofeedback, and surgery. However, these methods often have side effects, and patient satisfaction is still relatively low. A new approach needs to be explored to address this clinical problem.

The Disposable Gastrointestinal Vibrating Capsule System (Vibrabot capsule) (NMPA Device Approval No. 20223090282) is the world's first approved and marketed product for treating constipation through purely physical means. It can provide intermittent comfortable massages to the digestive tract, activate the intestinal neural network, awaken intestinal motility, and help alleviate constipation issues. Clinical study results show that the product is safe to use and can increase the frequency of bowel movements in patients with chronic functional constipation. This study focuses on post-marketing clinical study for patients with functional constipation of varying severity, further evaluating the efficacy of the product in a large sample population.

5. Product Features, Composition, Working Principle, and Action Mechanism

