7.1 Trial Procedure

7.1.1 Trial Flow Chart

| | Visit 1 (0~1 day) | Visit 2 (Week 2 ±3 days) | Visit 3 (Week 4 ±3 days) | Visit 4 (Week 6±3 days) | Visit 5 (Week 10 ±3 days) |
|--|-------------------|--------------------------|--------------------------|-------------------------|---------------------------|
| Informed Consent | X | | | | |
| Baseline Information | X | | | | |
| Inclusion/Exclusion Criteria | X | | | | |
| Prescription Vibrabot capsule treatment/Medication treatment | X | X | X | | |
| Guide patients to use the "Vibrabot Health" Official Account | X | | | | |
| Fill out the Baseline Period Questionnaire (including scale) in the Official Account | X | | | | |
| Fill out the Daily Bowel Movement Questionnaire and Constipation Symptom Self-Assessment Scale and Assessment Scale for Quality of Life with Constipation | | X | X | X | X |
| Concomitant treatment | X | X | X | X | X |
| Adverse event | X | X | X | X | X |

正常诊疗流程筛选入组
Screening for Inclusion Based on Normal Diagnosis and Treatment Procedure

| | | | | | |
|--|---|---|---------------------------------------|---|-------|
| 功能性便秘分型(结肠传输时间、肛门直肠测压等) Functional Constipation Subtyping (Colon Transit Time, Anorectal Manometry, etc.) | 通过症状或问诊对便秘分型初步评估 Preliminary Assessment of Constipation Subtype Based on Symptoms or Interview | 可选 Optional | | | |
| 通过评估, 选择其他治疗方法 Selecting Alternative Treatment Methods through Assessment | 使用蔚通胶囊治疗 Treatment with Vibrabot Capsule | | | | |
| 患者填写问卷, 收集数据 Patients Complete Questionnaires to Collect Data | 沪惠保优惠或其他渠道购买 Purchase through Shanghai-Huibo Health Benefits or Other Channels | | | | |
| 不同使用频次 Different Frequency of Use | 不同疗程 Different Treatment Duration | 与其他方法联合治疗 Combination Treatment with Other Methods | 不同严重程度 Various Severity Levels | 对比其他方法治愈 Comparing Treatment Efficacy with Other Methods | |
| 各中心医生端数据共享 Data Sharing among Medical Centers | 定期学术会议讨论 Regular Academic Meetings for Discussion | | | | |
| 蔚通治疗方法不断优化, 形成专家共识 Continuous Optimization of the Vibrabot Treatment Method, Leading to Expert Consensus | 完成总结报告、科技论文, 研究生培养 Completion of Summary Report, Scientific Paper, and Training of Graduate Students | | | | |

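### The 24-hour medication rule in the SBM/CSBM definitions removes movements from drug-treated patients only, so on-treatment counts in the drug and combination comparisons lean toward capsule alone

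*Combined protocol and SAP*

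**What the plan says.** The only definitions of the two outcome counts stand in the note to section 7 (Overall Design). The first is "Spontaneous bowel movement: No medication used within 24 hours before bowel movement". The second carries the same label but is evidently meant for CSBM: "No medication was used within 24 hours before defecation, and there is a feeling of complete fecal evacuation". Section 7 makes these two counts the measure of treatment effect for patients generally, not just for capsule patients.

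The word medication is not defined. Section 7 uses it in listing the data to collect: "baseline constipation status and treatment information, capsule intake during treatment, and concomitant medication". The flow chart in 7.1.1 uses it for the alternative to the capsule, in the row "Prescription Vibrabot capsule treatment/Medication treatment", which is marked at Visits 1 to 3. Secondary endpoint 9 uses the narrower pair laxative or enema.

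Section 3.1 gives as a purpose "to compare the efficacy with patients treated with drugs or other therapies during the same period", and also names combined medication as a factor to be analysed. Under section 3.2 patients "will undergo vibrating capsule treatment, other treatments, or combination therapy". At least 300 patients on other treatment are to be enrolled. The primary endpoint (7.2.1) concerns patients using the capsule alone, against 50%. Section 8 states one single-group hypothesis and no between-group test.

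**The concern.** A rule that discards movements soon after a laxative makes sense when the drug is rescue and the treatment under study is something else. Here a drug is also one of the treatments under study. The capsule is a physical device, listed apart from medication, so taking it does not trigger the exclusion. A prescribed constipation drug does.

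Followed as written, the rule measures the capsule by the movements that occur on treatment and measures a drug by the movements that occur away from it. A drug that works better than the capsule could be reported as working worse, and adding a drug to the capsule could appear to reduce its effect. The protocol intends its results to support consensus or guidelines, and a larger sample does not remove a measurement artefact.

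**Working it through.** **1. The plan's own figure.** The sample size is not in dispute. With p0 = 0.40, p1 = 0.50, two-sided α = 0.05 and power 0.80: [1.960·√0.24 + 0.842·√0.25]² / 0.10² = 190.7, so 191; 191/0.80 = 238.75, so 239. Both match section 8.1. The plan gives no figure for the comparison with drugs.

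**2. What the rule does to on-treatment counts.** Take medication to mean constipation drugs. If a drug is taken on k days a week, each dose blocks 24 hours and movements fall evenly over the week (assumptions), the share that can count is 1 − k/7.

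| k (days/week) | 0 | 1 | 2 | 3 | 5 | 7 |
|---|---|---|---|---|---|---|
| Countable share | 100% | 86% | 71% | 57% | 29% | 0% |

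A capsule-alone patient taking no such drug stays at 100%. At k = 7 the counted SBM and CSBM are zero. Then ≥3 SBM a week is impossible, and the change in CSBM is 0 minus baseline, which cannot reach +1. Endpoints 2, 3 and 4 are all missed whatever the true effect. This needs no simulation.

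**3. Endpoint 3 (≥3 SBM/week), illustration.** Assume true weekly rates that are gamma distributed with mean 4 and shape 4, and Poisson counts over 6 weeks. The proportion reaching 3 is 65% unmasked, 55% at 1/7 masked, 42% at 2/7, 27% at 3/7 and 0% with daily dosing. The unmasked level depends on the shape (56% at shape 2, 73% at shape 8), but the decline does not.

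**4. CSBM response, illustration.** Assume a baseline rate b, gamma with shape 2 and mean 0.5/week; the same true gain g for drug and capsule; counted on-treatment movements Poisson with mean 6(b + g)(1 − d), where d is the masked share; and a baseline counted over 1 or 2 weeks. A responder has a 6-week average minus baseline of at least 1. With a 2-week baseline, the percentages of responders are:

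| Baseline | g | d = 0 (capsule) | 1/7 | 2/7 | 3/7 | 1 |
|---|---|---|---|---|---|---|
| No drug | 1.0 | 56.3 | 43.5 | 29.9 | 17.1 | 0 |
| No drug | 2.0 | 91.3 | 83.7 | 71.5 | 53.7 | 0 |
| Same masking | 1.0 | 56.3 | 47.1 | 36.3 | 24.3 | 0 |
| Same masking | 2.0 | 91.3 | 86.5 | 78.7 | 65.6 | 0 |

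Over gains of 1.0 to 2.0 and both baseline lengths, with all comparators on drugs, the false capsule-alone advantage in points is:

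- no drug at baseline: 7–13 (1/7), 17–26 (2/7), 31–44 (3/7), 56–91 (daily);
- same masking at baseline: 4–9, 11–20, 21–33, 56–91.

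It shrinks in proportion to the drug-treated share: with daily dosing, 28–46 points if half of comparators are on drugs.

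**5. Rank reversal.** With a true gain of 1.5 on drug and 1.0 on capsule (2-week baseline), the true response is 79.5% v 56.3%. At 3/7 masking the drug shows 35.4% (no drug at baseline) or 46.2% (same masking), still against 56.3%.

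**6. Where the direction can turn.** In the same model (g = 1.0, 2-week baseline), a prior daily user whose baseline count was masked to zero, and who takes the drug one day in seven on study, responds 73% of the time. A capsule patient with no prior drug responds 56% of the time, so the lean is now against the capsule. If the capsule patient was also a prior daily user, the figure is 84% and the lean returns. The sign therefore depends on prior drug use in each group, which the documents do not give.

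**7. How far the ranges can be trusted.** The protocol has a single baseline questionnaire at Visit 1, not a counted baseline diary. If baseline is taken as known without error and unmasked, the gap is about 9–17 points at 1/7 and 42–59 at 3/7. The ranges in step 4 are illustrations, not bounds.

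**The case against.** The strongest reply concerns direction. Endpoints 2 and 4 involve change from baseline, and step 6 shows that drug use at baseline can reverse the lean. That stands. A reader might infer that every comparison with drugs is biased toward the capsule; the documents support this only for on-treatment counts, for endpoint 3 and for daily dosing.

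A second reply is that the comparison is non-randomised, driven by patient preference and without a planned test. That also stands and limits the harm to a stated purpose. Section 4 names non-drug comparators too ("The main treatments for constipation are adjusting lifestyle, medication, psychotherapy, biofeedback, and surgery"), and these are not affected.

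A third is that readers will take medication to mean rescue laxatives. The text does not say so, and 7.1.1 applies the word to the prescribed alternative.

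Two further inferences are tempting. One is that medication means any drug, so that patients on unrelated daily medicines lose movements and the primary response rate falls (a true 55% would read 55% × 0.90 = 49.5% if 10% took one daily). The contrast with the capsule in 7.1.1 makes this the less natural reading; it is a reason to define the term, not a demonstrated error. The other is that everything concerning capsule patients is untouched. That goes too far as well: combination patients receive the capsule, so they could enter endpoint 10 and the hypothesis in 8.1, which refers to vibrating capsule treatment and not to the capsule alone.

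Finally, a figure beside the note is not shown, and the questionnaire's counting logic is not given. Either might settle the matter in practice, but the printed definitions do not.

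**Conclusion.** The concern holds in this form. The rule as written removes treatment-period movements from patients taking constipation drugs, roughly in proportion to dosing days and completely with daily dosing, and removes none from capsule-alone patients who take no such drug. For endpoints 2 and 4 at less than daily dosing, the lean is toward capsule alone when baseline is unmasked or masked to the same degree; it can reverse in patients who reduce dosing on study. Follow-up endpoints 5 and 6 are affected only if the drug continues.

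The comparison bias does not enter the capsule-alone primary endpoint. The size is unknown, because drug share, dosing frequency and counting logic are not given; the figures above rest on assumed rates and gains. It should be fixed because a stated purpose depends on these counts and the correction is cheap.

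**What to change.** 1. In the section 7 note, define medication as any drug or enema given for constipation, so that unrelated medicines do not remove movements. Label the second definition CSBM.
2. For comparisons with drug-treated patients and for combination therapy, make complete bowel movements per week, and total bowel movements, counted regardless of medication, the comparative measure. Use the same rule at baseline and on treatment, and report PAC-SYM and PAC-QOL beside it.
3. Keep CSBM for the capsule-alone primary endpoint, apply the same counting rule to the baseline questionnaire, and report the medication-independent count as a sensitivity analysis.
4. Confirm that the questionnaires record every movement and the timing of medication.

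Exempting only the study-period drug would not do. Baseline would stay masked, and in the model above a patient continuing the same daily drug at an unchanged 0.5 CSBM a week would be called a responder about 16% of the time, against 4–7% when both periods are counted alike.

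The cost is definition and SAP wording with no new visits, plus questionnaire fields if item 4 finds a gap. The downside is that the medication-independent count also credits movements induced by rescue, and the capsule's apparent advantage over drugs may shrink.

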7.1 Trial Procedure

7.1.1 Trial Flow Chart

| | Visit 1 (0~1 day) | Visit 2 (Week 2 ±3 days) | Visit 3 (Week 4 ±3 days) | Visit 4 (Week 6±3 days) | Visit 5 (Week 10 ±3 days) |
|--|-------------------|--------------------------|--------------------------|-------------------------|---------------------------|
| Informed Consent | X | | | | |
| Baseline Information | X | | | | |
| Inclusion/Exclusion Criteria | X | | | | |
| Prescription Vibrabot capsule treatment/Medication treatment | X | X | X | | |
| Guide patients to use the "Vibrabot Health" Official Account | X | | | | |
| Fill out the Baseline Period Questionnaire (including scale) in the Official Account | X | | | | |
| Fill out the Daily Bowel Movement Questionnaire and Constipation Symptom Self-Assessment Scale and Assessment Scale for Quality of Life with Constipation | | X | X | X | X |
| Concomitant treatment | X | X | X | X | X |
| Adverse event | X | X | X | X | X |

正常诊疗流程筛选入组
Screening for Inclusion Based on Normal Diagnosis and Treatment Procedure

| | | | | | |
|--|---|---|---------------------------------------|---|-------|
| 功能性便秘分型(结肠传输时间、肛门直肠测压等) Functional Constipation Subtyping (Colon Transit Time, Anorectal Manometry, etc.) | 通过症状或问诊对便秘分型初步评估 Preliminary Assessment of Constipation Subtype Based on Symptoms or Interview | 可选 Optional | | | |
| 通过评估, 选择其他治疗方法 Selecting Alternative Treatment Methods through Assessment | 使用蔚通胶囊治疗 Treatment with Vibrabot Capsule | | | | |
| 患者填写问卷, 收集数据 Patients Complete Questionnaires to Collect Data | 沪惠保优惠或其他渠道购买 Purchase through Shanghai-Huibo Health Benefits or Other Channels | | | | |
| 不同使用频次 Different Frequency of Use | 不同疗程 Different Treatment Duration | 与其他方法联合治疗 Combination Treatment with Other Methods | 不同严重程度 Various Severity Levels | 对比其他方法治愈 Comparing Treatment Efficacy with Other Methods | |
| 各中心医生端数据共享 Data Sharing among Medical Centers | 定期学术会议讨论 Regular Academic Meetings for Discussion | | | | |
| 蔚通治疗方法不断优化, 形成专家共识 Continuous Optimization of the Vibrabot Treatment Method, Leading to Expert Consensus | 完成总结报告、科技论文, 研究生培养 Completion of Summary Report, Scientific Paper, and Training of Graduate Students | | | | |

7.1.2 Visit Content

Each patient will undergo a series of study visits, including screening, treatment visit, and follow-up visit. The visit process is briefly described as follows:

Visit 1 (0 ~ 1 day) - Baseline/Screening Period:

This visit includes:

The patient will sign an informed consent form;

Set the inclusion/exclusion criteria;

Guide patients to fill out the questionnaire using the Official Account and complete the *Baseline Period Questionnaire* in the Official Account.

Prescription Vibrabot capsule treatment or other treatment options.

Visit 2 (Week 2 ±3 days) - Treatment Period 1:

This visit includes:

Fill out the *Daily Bowel Movement Questionnaire* in the WeChat Official Account every day, take Vibrabot capsules on time or opt for other treatment plans;

Fill out the *Constipation Symptom Self-Assessment Scale and Assessment Scale for Quality of Life with Constipation* in the Official Account every 2 treatment weeks.

Record adverse events and concomitant treatments;

Prescription Vibrabot capsules or other treatment options.

Visit 3 (Week 4±3 days) - Treatment Period 2

This visit includes:

Fill out the *Daily Bowel Movement Questionnaire* in the WeChat Official Account every day, take Vibrabot capsules on time or opt for other treatment plans;

Fill out the *Constipation Symptom Self-Assessment Scale and Assessment Scale for Quality of Life with Constipation* in the Official Account every 2 treatment weeks.

Record adverse events and concomitant treatments;

Prescription Vibrabot capsules or other treatment options.

Visit 4 (Week 6 ±3 days) - Treatment Period 3

This visit includes:

Fill out the *Daily Bowel Movement Questionnaire* in the WeChat Official Account every day, take Vibrabot capsules on time or opt for other treatment plans;

Fill out the *Constipation Symptom Self-Assessment Scale and Assessment Scale for Quality of Life with Constipation* in the Official Account every 2 treatment weeks.

Record adverse events and concomitant treatments.

Visit 5 (Week 10±3 days) - Follow-up Period:

This visit includes:

Fill out the *Daily Bowel Movement Questionnaire* in the WeChat Official Account every day;

Fill out the *Constipation Symptom Self-Assessment Scale and Assessment Scale for Quality of Life with Constipation* in the Official Account every 2 treatment weeks;

Record adverse events and concomitant treatments.

